2.1 Data analysis general information

Novartis and/or a designated CRO will perform all the analyses. Any additional data analyses performed independently by any investigator should be submitted to Novartis before publication or presentation. The end of study is defined as the earliest occurrence of one of the following:

- All patients have died or discontinued from the study
- Another clinical study or patient support programs becomes available that can continue to provide Afinitor in this patient population and all patients ongoing are eligible to be transferred to them
- Afinitor has been approved for this indication in combination with Exemestane

The final analysis for safety and efficacy will be conducted at the end of the study. All available data from all patients up to this cutoff date will be analyzed per protocol.

SAS® version 9.4 or later will be used in all analyses.

2.1.1 General definitions

Study drug is defined as everolimus, or matching placebo. **Study treatment** is defined as everolimus + exemestane or placebo + exemestane.

2.1.2 Date of first administration of study drug

The date of first administration of study drug is derived as the first date when a non-zero dose of study drug is administered and recorded on the dose administration record (DAR) eCRF. For the sake of simplicity, the date of first administration of study drug will also be referred to as the start of study drug.

2.1.3 Date of last administration of study drug

The date of last administration of study drug is defined as the last date when a non-zero dose of study drug is administered and recorded on the DAR eCRF.

2.1.4 Date of first administration of study treatment

The date of first administration of study treatment is derived as the first date when a non-zero dose of any component of study treatment is administered and recorded on the DAR eCRF. For the sake of simplicity, the date of first administration of study treatment will also be referred to as the start of study treatment.

2.1.5 Date of last administration of study treatment

The date of last administration of study treatment is defined as the last date when a non-zero dose of any component of study treatment was administered and recorded on the DAR eCRF.

2.1.6 Study day

The study day for safety assessments (e.g., adverse event onset, laboratory abnormality occurrence, vital sign measurement, dose interruption, etc.) will be calculated as the difference between the date of the assessment and the start of study treatment plus 1. (Note: except in the case when the assessment is before start of study treatment in which case study day is calculated as the difference between the date of the assessment and the start of study treatment. In this particular case, the study day displayed on the listing will be negative.)

The study day for all other, i.e., non-safety assessments (tumor assessment, death, disease progression, tumor response, ECOG performance status) will be calculated as the difference between the date of the event and the randomization date plus 1. In other words, all efficacy time-to-event variables (e.g., progression-free survival, overall survival, time to response) will be calculated from date of randomization. (Example: if randomization date is 02JAN2007, start of study drug is on 05JAN2007, and the date of death is 09JAN2007, then the study day when death occurred is 8.)

The study day will be displayed in data listings.

2.1.7 Baseline

Baseline value(s) is (are) the result of an investigation describing the “true” uninfluenced state of the subject.

For **efficacy evaluations**, the last available assessment before or at the date of randomization is taken as ‘baseline’ value or ‘baseline’ assessment. In the context of the definition of baseline,

efficacy evaluations also include the ECOG performance status, subject-reported outcome measures and clinical measurements included in the stratification.

For **safety evaluations** (i.e., laboratory and vital signs), the last available assessment before or at the date of the start of study treatment is taken as ‘baseline’ assessment.

2.1.8 On-treatment assessment/event

On-treatment assessment/event is defined as any assessment/event obtained in the time interval:[date of first administration of study treatment; date of last administration of study treatment + 30 days], i.e., including the lower and upper limits. (Note: The calculation of study treatment duration, however, may use different rules as specified in [Section 2.4.1](#).)

2.1.9 Last contact date

The last contact date will be derived for subjects not known to have died at the final analysis cut-off using the sources presented in [Table 2-1](#) below:

Table 2-1 Last contact date data sources

Source data	Condition
Last contact date/last date subject was known to be alive from survival follow-up page	Subject status is reported to be alive. Do not use if subject status is reported unknown.
Start/End dates from further antineoplastic therapy	Non-missing medication/procedure term.
Start/End dates from drug administration record	Non-missing dose. Doses of 0 are allowed.
End of treatment date from end of treatment page	No condition.
Tumor (RECIST) assessment date	Evaluation is marked as ‘done’.
Laboratory collection dates	Sample collection marked as done.
Vital signs date	At least one non-missing parameter value.
Performance status date	Non-missing performance status.
Start/End dates of AE	Non-missing verbatim term.

The last contact date on or before the data cut-off date should be used; the cut-off date should not be used as the censoring date (even in presence of post cut-off data) unless the subject was seen or contacted on the cut-off date.

Imputed dates (e.g., analysis cut-off date programmatically imputed to replace the missing end date of a dose administration record) will not be used to derive the last contact date. Partially imputed dates (i.e., only day or day and month imputed) are allowed to be used for last contact date only if coming from Survival Follow-up page.

The last contact date will be used for censoring of subjects in the analysis of overall survival.

2.2 Analysis sets

The Full Analysis Set (FAS) comprises all subjects to whom study treatment has been assigned by randomization. According to the intent to treat principle, subjects will be analyzed according to the treatment and strata they have been assigned to during the randomization procedure.

The Safety Set (SAF) consists of all subjects who received at least one dose of study treatment. Subjects will be analyzed according to treatment actually received, where treatment received is defined as the randomized treatment if the subject took at least one dose of that treatment or the first treatment received if the randomized treatment was never received.

The actual treatment received corresponds to:

- the randomized treatment if subjects took at least one dose of that treatment
- the first treatment received if the randomized treatment was never received

2.2.1 Subgroup of interest

Not Applicable.

2.3 Subject disposition, demographics and other baseline characteristics

Subjects who sign an informed consent but fail to be started on treatment for any reason will be considered a screen failure. The reason for not being started on treatment will be entered on the Screening Phase Disposition Page. The demographic information, informed consent, and Inclusion/Exclusion pages must also be completed for Screen Failure Subjects. A summary of the demographic, baseline disease characteristics and prior antineoplastic therapy of the study population was provided in the primary CSR [Study Y2202-Section 10.4].

2.3.1 Subject disposition

The Full Analysis Set will be used for subject disposition summaries. Based on the two eCRF pages 'End of Treatment' and 'End of Post Treatment Disposition eCRF page' there will be one combined summary, stratified by treatment, showing:

- Number (%) of subjects who discontinued the study treatment (based on the 'End of Treatment' page);
- Reasons for study treatment discontinuation (based on the 'End of Treatment' page).
- Number (%) of subjects who entered the post-treatment evaluation phase (based on the 'End of Treatment' page);
- Number (%) of subjects who discontinued from the post-treatment evaluations (based on the 'End of Post Treatment Disposition eCRF page' page);
- Reasons for discontinuation from the post-treatment evaluations phase (based on the 'End of Post Treatment Disposition eCRF page' page).

2.4 Treatments (study treatment, rescue medication, concomitant therapies, compliance)

2.4.1 Study treatment / compliance

Duration of study treatment exposure, cumulative dose, dose intensity (DI) and relative dose intensity (RDI) will be summarized by treatment. In addition, the duration of exposure to study treatment will be categorized into time intervals; frequency counts and percentages will be presented for the number of subjects in each interval. The number of subjects, who have dose reductions or interruptions, and the reasons, will be summarized by treatment.

Listings of all doses of the study treatment along with dose change reasons will be produced.

The Safety Set will be used for all summaries and listings of study treatment.

2.4.2 Duration of study treatment exposure

The following algorithm will be used for everolimus and exemestane to calculate the duration of study treatment exposure for subjects who took at least one dose of any of the components of the study treatment:

Duration of exposure (days) = (date of last administration of study treatment) – (date of first administration of study treatment) + 1.

Total duration of exposure will be derived as the sum of the cycle duration of exposure.

The duration includes the periods of temporary interruption (of any component of the study treatment for any reason).

Duration of exposure to each component of the study treatment will also be calculated.

2.4.3 Cumulative dose

Cumulative dose is defined as the total dose given during the study treatment exposure period and will be summarized for each of the study treatment components separately. For subjects who do not receive any drug, the cumulative dose will be set to zero.

2.4.4 Dose intensity and relative dose intensity

Dose intensity (DI) for subjects with non-zero duration of exposure is defined as follows:

DI (dosing unit / unit of time) = Cumulative dose (dosing unit) / Duration of exposure (unit of time).

For subjects who do not receive any drug, the DI will be set to zero.

Planned dose intensity (PDI) is the assigned dose by unit of time planned to be given to subjects as per protocol in the same dose unit and unit of time as that of the Dose Intensity.

Relative dose intensity (RDI) is defined as follows:

RDI = DI (dosing unit / unit of time) / PDI (dosing unit / unit of time).

DI and RDI will be summarized separately for each of the study treatment components, but using the duration of the study treatment exposure, not the duration of exposure to each of the components.

2.4.5 Dose reductions or interruptions

The number of subjects, who have dose reductions or interruptions, and the reasons for such reductions/interruptions, will be summarized separately for each of the study treatment components.

An interruption is defined as a 0 mg dose given on one or more days. However, for last records, it will be counted as an interruption only if there are 2 or more last records with 0 mg dose.

If a subject moves from a dose level that is higher than the studied dose under the protocol to the dose level that is being studied in the protocol, such changes will not be counted as reductions. However, if any subject moves directly from a higher than studied dose down to a lower than protocol-studied dose, or to the dose level being studied under the protocol but on a less frequent regimen, such changes will be counted as reductions. If first dose is lower than the studied dose under the protocol, it will be counted as a dose reduction.

For everolimus and exemestane, reductions count should be based on the actual total daily dose (mg).

If one drug is permanently discontinued (before a protocol-planned discontinuation date) while the other is ongoing, such discontinuations will be classified as interruptions.

Dose reductions and interruptions will be tabulated both separately and in a combined fashion. In the combined summary, dose interruptions will be considered as dose reductions to 0 mg, and therefore all reductions/interruptions will be labeled as reductions and tabulated in one table.

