#### 6.1.4 Guidelines for continuation of treatment

For guidelines for continuation of treatment, refer to [Section 6.3 Dosing modifications](#).

Patients who permanently discontinue one of the study treatments for any reason other than disease progression may continue the other study treatment as part of the trial therapy at the investigators discretion until disease progression, unacceptable toxicity, death or discontinuation from study treatment due to any other reason and should follow the protocol safety and efficacy assessments as scheduled. After discontinuing study treatment, further treatment is left to the physician's discretion.

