#### **10.5.2.6 Tolerability**

Tolerability of study treatment will be assessed by summarizing the number of dose interruptions and dose reductions. Reasons for dose interruption and dose reductions, cumulative dose and dose intensity will be listed by patient.

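### The SAP counts a permanent stop of one drug as an interruption, so the tolerability tables mix permanent stops with temporary holds

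*SAP*

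**What the plan says.** Protocol 6.1.4 permits the situation: "Patients who permanently discontinue one of the study treatments for any reason other than disease progression may continue the other study treatment", at the investigator's discretion and with assessments continuing on schedule.

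SAP 2.4.5 says how it is counted. When one drug is stopped for good, ahead of any stop date planned in the protocol, and the other continues, "such discontinuations will be classified as interruptions". It plans the tables in two forms: "Dose reductions and interruptions will be tabulated both separately and in a combined fashion". In the combined form an interruption is treated as a reduction to 0 mg, and "all reductions/interruptions will be labeled as reductions and tabulated in one table". A further rule covers the end of the dosing record: "for last records, it will be counted as an interruption only if there are 2 or more last records with 0 mg dose".

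Protocol 10.5.2.6 names the measure that these tables serve: "Tolerability of study treatment will be assessed by summarizing the number of dose interruptions and dose reductions".

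The disposition summary in SAP 2.3.1 gives the "Number (%) of subjects who discontinued the study treatment" with reasons. SAP 2.1.1 defines study treatment as the combination, and study drug as everolimus or placebo alone.

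**The concern.** Safety and tolerability of the combination is a secondary objective, and the dose-modification tables are the protocol's stated way of assessing tolerability. A hold that resolves and a drug that is never restarted are different outcomes, and the protocol treats them differently:

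- Table 6-3 has separate instructions for temporary interruption and for discontinuing everolimus.
- Protocol 6.3.1 limits how long an interruption may last before discontinuation is required.
- The adverse event form in Protocol 8.1.1 has separate entries for a drug that is interrupted and one that is withdrawn.

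SAP 2.4.5 merges the two outcomes in the tables. A reader of the final report who sees a count of everolimus interruptions cannot say how many of those patients came back on drug. Interruption counts will include permanent stops, and the all-cause count of permanent everolimus/placebo stops, a basic tolerability figure for an add-on drug, will be missing.

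**Working it through.** There is no figure in the plan to reproduce. The check is to follow one case through every planned output: everolimus/placebo stopped for good, exemestane continued.

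**Can the case arise?** Yes. Protocol 6.1.4 allows it, and several toxicity entries name everolimus alone as the drug to discontinue (for example, in Table 6-3, grade 4 febrile neutropenia and grade 4 other non-haematologic toxicity). Protocol 6.1.5 also lists investigator or patient discretion as a reason to stop treatment, so causes other than adverse events are foreseen.

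**Where does it appear?**

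1. *Separate interruption table (SAP 2.4.5).* Counted as an interruption, by component and with reasons, but in the same category as a temporary hold.
2. *Combined table (SAP 2.4.5).* Labelled a reduction, because an interruption is taken as a reduction to 0 mg.
3. *Disposition (SAP 2.3.1 with 2.1.1).* By the wording, not counted at the time of the stop, because study treatment means the combination. SAP 2.1.5 points the same way: the last administration of study treatment is the last non-zero dose of any component.
4. *Adverse event tables (SAP 2.8.1.4).* If an adverse event was the cause, the stop appears in the tables of events leading to study drug discontinuation (one for all causality, one for suspected relationship). Study drug is everolimus or placebo, so these tables fit the case. If the cause was anything else, the stop does not appear.
5. *Exposure by component (SAP 2.4.2).* Everolimus duration is shorter than study treatment duration.
6. *Relative dose intensity (SAP 2.4.4).* The denominator is the whole study treatment duration. With d days on everolimus at 10 mg and T days of study treatment, dose intensity is 10d/T mg per day. Dividing by the planned 10 mg per day gives a relative dose intensity of d/T. An early stop makes d smaller than T, so the value falls.
7. *Dose listings (SAP 2.4.1).* The stop is shown with its reason, patient by patient.

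**What is missing?** Items 1 and 2 count the patient but do not identify the stop as permanent. Item 4 identifies it only when an adverse event caused it. Items 5 and 6 reflect it without counting it. Item 7 is not a summary. By the wording, no summary gives the number of permanent everolimus/placebo stops for any reason, by arm. For exemestane stopped while everolimus/placebo continues, the study drug tables in item 4 do not apply by definition.

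**Is the counting rule itself clear?** Not fully. If a permanent stop is recorded as one final 0 mg record, or simply as no further record, the last-records rule would leave it out while the permanent-stop rule would count it. The SAP does not say which rule takes precedence, so two programmers could obtain different counts.

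**The case against.** The strongest reply is that little is hidden. Adverse-event-driven everolimus stops, the main tolerability signal, are tabulated as discontinuations by system organ class and preferred term. Reductions and interruptions are also tabulated separately, so the reduction label is confined to a combined table whose definition is stated. Component exposure, relative dose intensity and the listings all reflect an early stop. The SAP also covers the final report, after the primary report and after approval of the indication, and the primary report may have given component discontinuations; it is not available here. All of this stands, and it limits the point to misclassification plus a missing all-cause total.

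It may also be said that disposition could capture the stop. That depends on whether the End of Treatment page is completed per component, which the documents do not state. The point therefore rests on the SAP's wording.

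A reader might go further and infer that the rule makes everolimus look better tolerated than it is. The documents do not support that. Permanent stops raise the interruption count and the combined reduction count, and they lower everolimus relative dose intensity; each of these counts against everolimus.

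A reader might also infer that the problem falls mainly on the everolimus arm, or put a number on it. Assuming that 10% to 25% of about 80 everolimus patients (160/2) stop everolimus first would give 0.10 × 80 = 8 to 0.25 × 80 = 20. Nothing in the documents supplies that rate for either arm, some toxicity rules send the patient off study treatment altogether, and such a total would include stops already tabulated in SAP 2.8.1.4.

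**Conclusion.** The point holds as a reporting fault. The rule in SAP 2.4.5 places permanent single-drug stops in the same category as temporary holds, in the tables that the protocol names as its tolerability measure. Stops not caused by an adverse event are not summarised as discontinuations, and no all-cause count by arm is planned. The patients are not lost, since they remain in the interruption counts.

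The size is unknown and cannot be derived from the documents, and neither can the direction of any bias. The conclusion assumes that disposition follows the SAP's definition of study treatment; if the End of Treatment page is completed for each drug, the gap is smaller. The PFS analysis does not use these counts and is unaffected. The change is worth making because it is cheap and corrects a count that the protocol relies on.

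**What to change.** In SAP 2.4.5, replace the permanent-stop rule with a separate category: number and percentage of subjects who permanently discontinued everolimus/placebo while exemestane continued, and the reverse, by arm and reason. Show it within the tolerability summary, so that these patients stay in the protocol's measure, but apart from temporary interruptions. Flag it separately in the combined reduction table. State how a permanent stop is identified when the dosing record ends in a single 0 mg entry or in no further entry, so that the last-records rule no longer competes with it.

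Dosing records and reasons for dose changes are already planned outputs, so no new data collection appears necessary. The cost is one extra table section and a change from the counting rule now written in the SAP; interruption counts would no longer be directly comparable with any earlier table produced under the present rule.

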2.4.6 Prior, concomitant and post therapies

Concomitant therapy is defined as all interventions (therapeutic treatments and procedures) besides the study treatment that were administered to a subject, preceding or coinciding with the study assessment period (within 28 days prior to the study treatment through 30 days after the last dose of study treatment).

Concomitant medications entered into the database will be coded using the WHO Drug Reference List to allow for categorization by preferred term. In addition to categorizing medication data by preferred term, drugs will be classified according to their ATC classification in order to present and compare how they are being utilized.

Concomitant medications and significant non-drug therapies taken concurrently with the study drug(s) will be listed and summarized by ATC class, preferred term and treatment arm by means of frequency counts and percentages. These summaries will include medications starting on or after the start of study treatment or medications starting prior to the start of study treatment and continuing after the start of study treatment.

Prior concomitant medications or significant non-drug therapies starting and ending prior to the start of study treatment were summarized in the primary CSR and will not be repeated for the final CSR.

The Safety Analysis Set will be used for all concomitant medication tables and listings.

2.4.7 Inducers, inhibitors and substrates of CYP3A

Everolimus is a substrate of CYP3A4, and a substrate and moderate inhibitor of the multidrug efflux pump, PgP (PgP, MDR1, and ABCB1). Extent of absorption and subsequent elimination of systemically absorbed everolimus may be influenced by products that are substrates, inhibitors, or inducers of CYP3A4 and/or PgP. Therefore:

- Co-administration with strong inhibitors of CYP3A4 or PgP should be avoided;
- Co-administration with moderate CYP3A4 inhibitors (e.g., erythromycin, fluconazole) or PgP inhibitors should be used with caution;
- Seville orange, star fruit, grapefruit and their juices affect CYP3A4 and PgP activity concomitant use should be avoided.

Please refer to Table 6-8 of the protocol for the list of relevant inducers and inhibitors of CYP3A and to Table 6-9 of the protocol for the list of relevant substrates, inducers, and inhibitors of PgP. Despite the fact that some of these drugs should be avoided completely and some used with caution, there may be subjects who took these drugs during the study. In that case, the concomitant medications need to be identified and classified as protocol deviations (review to be performed by a Clinical Pharmacologist) and then tabulated and/or listed in the Clinical Study Report as appropriate.

